7.3.4 Aspirin, other anti-coagulants, and anti-platelet aggregates

- Aspirin and other anti-coagulants are only prohibited in the first 5 role-out patients until the effects of LEAG on platelet function can be assessed.

8.0 ASSESSMENT INSTRUMENTS

8.1 Gail score (Appendix D)

Age, race, age at menarche, age at first live birth, number of first degree relatives with breast cancer, number of breast biopsies and presence of atypical ductal hyperplasia will be entered into a Gail score calculation program (Appendix D) (National Cancer Institute Breast Cancer Risk Assessment Tool online calculator at www.cancer.gov/bcrisktool/). The resulting score represents a patient's 5-year cumulative risk of breast cancer. A risk greater than 1.66% is the threshold for chemoprevention trials.

8.2 Tecumseh Occupational and Minnesota Leisure Time Activity Questionnaires (Appendices A and B)

Both occupational and leisure time exercise exposure for the prior 12 months will be measured by the Tecumseh and Minnesota occupational and leisure time activity questionnaires. The validity and reliability of the Tecumseh Occupational Activity Questionnaire (43) has been documented by Ainsworth (44, 45). Leisure time physical activity will be measured by the Minnesota Leisure Time Activity Questionnaire which has also been previously tested for validity and reliability and is a well-accepted measurement tool (43). Of note, the use of the Tecumseh and Minnesota Occupational and Leisure Time Surveys allow for calculation of energy expenditure. Specifically, each activity recorded on the survey will be assigned a calculated metabolic equivalent (MET) value based on the published compendium of physical

activity (46). This MET value will be multiplied by the number of hours spent in each activity per week (i.e. METs x hrs/wk). This variable (METs x hrs/wk) will then be analyzed for the study group as a continuous variable and in quartiles.

8.3 National Cancer Institute Dietary History Questionnaire (Appendix C)

The current proposal will utilize the Dietary History Questionnaire (DHQ) developed by the Risk Factor Monitoring and Methods Branch (RFMMB) of the National Cancer Institute. The *Eating at America's Table Study* conducted by the RFMMB compared their new DHQ with the previous standard Block and Willet food frequency questionnaires (FFQs). The DHQ performed best of all in a randomized sample of 1,640 men and women (47). The DHQ is a self-administered questionnaire that represents a refinement over the RFMMB Block FFQ, with improved comprehension across various economic and ethnic groups and increased attention to dietary constituents of interest in disease prevention: fiber, energy, carotenoids and vitamin A, E and C. The questionnaire will be entered into an ASCII text file and analyzed using Diet*Calc Version 1.2 free downloadable software. Energy intake (kcal/kg), refined carbohydrate, fat, and fruit and vegetable intake (% of total intake) will be analyzed as continuous variables and by quartiles.

9.0 LABORATORY TESTS AND METHODS

9.1 Blood Collection

Collection of blood for inflammatory mediators and HOMA index must occur within 2 weeks of treatment. Participants will have blood drawn prior to starting ginseng and on the day of surgery.

A. Fasting Blood Draw (NPO after midnight):

1. Draw 40 cc blood from a vein into vacutainer tubes: 6mL in EDTA, 6mL in Na Heparin, 5mL in clot activator tube, and 24mL in serum tubes. (Serum tubes to be refrigerated (4°C) until centrifuged, and then serum will be aliquoted into 1ml cryotubes).
2. An additional 2 tubes of blood with citrate will be drawn on the first five patients for the Platelet Function Assay-100. – See section 5.7.4
3. Serum for ginsenoside levels and inflammatory proteins stored in -80°C freezer in lab prior to shipping to Carbondale laboratory.
4. Analyze serum for HOMA index, leptin, ghrelin, adiponectin, and angiopoietin.

5. Analyze serum for gRc and gRh2, IL1b, IL6, IL8, MCP-1, TNFa, HGF, NGFb, insulin, leptin.

B. Inflammatory Serum Protein Panel (LINCOpex) and Serum Adipokine Panel

Serum levels of TNFa and IL6 are elevated in patients who are obese or hyperinsulinemic and play an important role in the pathogenesis of type II diabetes. These serum markers also declined in insulin-resistant individuals who participated in an exercise program (48). In a study of adipokine expression in cancer patients, breast and colorectal cancer patients had blood plasma levels of insulin, TNF-alpha and breast epithelial expression of estrogen and progesterone receptors higher than controls. In the same study, breast cancer patients, but not colorectal cancer patients, had plasma levels and adipose tissue expression of leptin significantly higher than controls, associated with elevated values of estrogen and progesterone-receptors (49). These serum markers can be assayed simultaneously in a multiplex immunoassay (human adipokine panel B, LINCO, St. Louis, MO) using Luminex technology. The assay will be performed by the SIU Cancer Institute Molecular Core Facility. Serum adipokine levels of breast cancer patients before and after ginseng treatment will be compared. Serum will be collected and stored at -80°C until the assay is performed.

High serum angiopoietin-2 levels have been associated with tumor burden, stage of disease, and metastatic spread. Pre-LEAG serum levels will be compared with post-LEAG serum levels of enroll patients. ELISA assays will be use to batch the samples and perform angiopoiten-2 analysis.

C. High performance Liquid Chromatography-Mass Spectrophotometry

The concentrations of G2, grh in serum will be measured using liquid chromatography followed by tandem mass spectrometry. This combination is able to provide excellent sensitivity, speed and offers positive compound identification through the use of multiple reaction monitoring (MRM). Prior to analysis, samples of gRc and gRh2 will be analyzed using tandem mass spectrometry to determine the characteristic fragmentation pattern of each compound. During analysis, the mass spectrometer will be set up to monitor only signals corresponding to the molecular weights of the two compounds of interest. The instrument will then fragment each compound and indicate whether the fragmentation pattern matches the previously recorded one. This method is used often for monitoring specific compounds in complex samples, such as the detection of steroid use in athletes. It provides a positive identification through accurate mass measurement followed by a characteristic fragmentation pattern. Absolute quantification is calculated by either measuring a calibration curve with known samples or by using an internal standard.

D. Risks and side effects for Blood Tests

- | Likely | Unlikely |
|---|--|
| 
• Slight discomfort and/or pain when drawing blood• Bruising at the site• Minor bleeding at the site (just after sample is drawn) | 
• Infection at the site• Fainting |

E. Immunocytochemistry

Unstained paraffin-embedded sections from the diagnostic biopsy and the resected specimen including tumor and histologically normal breast epithelium will be subjected to immunostaining using a streptavidin-peroxidase technique. Briefly, permeabilized sections will have endogenous peroxidase activity blocked with 1X blocking solution (Kirkegaard & Perry Laboratories, Gaithersburg, MD) and the antigen unmasked by incubating in 10mM citrate buffer, pH 6.0 for 5 min at 95° C and rinsing with TBS. Nonspecific binding of the secondary antibody will be blocked with normal goat serum for 15 min, then sections will be incubated with a 1:50 dilution of rabbit anti-human COX-2 polyclonal antibody (Santa Cruz Biotechnology, Inc., Santa Cruz, CA), or cyclin D1 (Labvision). Immunoperoxidase staining will be performed using a biotin/streptavidin peroxidase complex (HistoMark™ Kirkegaard & Perry Laboratories, Gaithersburg, MD) and DAB substrate (Research Genetics, Huntsville, AL). Sections will be counterstained with hematoxylin. Fetal kidney tissue will be used as a positive control, and the primary antibody will be replaced with normal rabbit serum as a negative control. The ER, PR, and Ki67 staining will be done in the pathology department of the hospital where the diagnostic biopsy was performed, in order to optimally compare baseline and treated tumor.

F. In situ TUNEL

Unstained paraffin-embedded sections from the diagnostic biopsy and the resected specimen including tumor and histologically normal breast epithelium will be assayed for apoptosis by terminal deoxynucleotidyl transferase-mediated dUTP-biotin nick end-labeling (TUNEL). 5 µm sections will be deparaffinized and rehydrated in ethanol followed by an antigen retrieval step consisting of boiling in 0.01 M sodium citrate buffer for 2 min. Sections will be incubated with proteinase K (6.2 µg/ml; Boehringer Mannheim, Indianapolis, IL) followed by TdT (300 enzyme units/ml, Pharmacia Biotec, Piscataway, NJ) and Bio-14-dATP (0.94nM, GIBCO-BRL, Life Technologies). Biotinylated ATP will be detected using the ABC staining method (Vector Laboratories). As a positive control, slides will be pre-treated with DNase (20K units/ml; Sigma Biosciences, St. Louis, MO). Cells will be counted as TUNEL-positive if their nuclei

fluoresce and display typical apoptotic morphology with chromatin condensation. The number of apoptotic cells will be defined as the number of TUNEL-positive cells per field after counting 20 sequential fields at 250X.

G. Assessment of oxidative stress by MDA Assay

This assay will be used to determine the amount of lipid peroxidation by the malondialdehyde (MDA) levels as described by Ohkawa (50). Approximately 1 gm of tumor and normal breast tissue will be harvested, weighed and homogenized with a glass homogenizer in 1:10 wt:wt PBS. BHT will be added to the homogenates to arrest further oxidation and the homogenates will be stored at -80°C. The homogenates will then be analyzed for thiobarbituric acid reactive substances (TBARS) using commercially available assay kit from Zeptometrix. Briefly, mammary homogenate will be added to 8.1% SDS and vortexed. Thiobarbituric acid will then be added and placed in 95° C water bath for 60 minutes. The samples will be cooled to room temperature and centrifuged at 3000 rpm for 15 minutes. Supernatants from experimental samples and MDA standards will be measured by fluorescence excitation at 530 nm and emission at 550 nm.

9.2 Pathology Studies

9.2.1. Tissue Needed

- 10gm segment of grossly normal tissue processed for paraffin embedded slides
- 10gm segment of tumorous tissue processed for paraffin embedded slides
- Pathology slides stained for ER, PR, Ki67 and inked for margins
- Unstained sections processed for SIU lab for cyclin D1 and cyclin D2, COX-2, and TUNEL

9.2.2 Procedure

On the day of surgery, the breast tissue will be submitted to the pathologist and inked for margins per routine. The tissue will be sectioned and margins studied per routine. From the grossly normal breast tissue that would be otherwise discarded, a 20 gm segment will be frozen for oxidative stress MDA assay, and a 10 gm segment will be processed for paraffin-embedded slides. The tumor will be processed as paraffin-embedded slides per routine diagnostic stains. Tumor and normal breast

slides will be stained for ER, PR, and Ki-67 in the pathology dept of the hospital where the surgery takes place. Unstained paraffin sections of tumor and normal breast will be allocated to [name] lab for immunohistochemical staining for cyclin D-1, cyclin D-2, COX-2 and TUNEL. These sections will be cut from tissue remaining in paraffin blocks after adequate diagnostic studies have been completed.

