1.0 OBJECTIVES

1.1 Primary Objectives

Analyze biomarker *in vivo* response of breast cancer tumors and surrounding normal breast epithelial cells to preoperative treatment with gelatin encapsulated lyophilized water-extract of American Ginseng root (LEAG).

- 1.1.1 The diagnostic core biopsy will be compared to the operative specimen for effects on the following proliferative and tumor biomarkers: immunohistochemistry for ER, PR, Ki67, cyclin D1, COX-2.

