Our existing study, the Surrogate Endpoints and Lifestyle Factors (SELF) trial, has as its goal to analyze the prevalence in women seeking risk assessment for breast cancer, of insulin resistance, central obesity, and proliferative changes in mammary ductal cells, and determine whether these potential surrogate endpoint biomarkers (SEBs) have a positive correlation with breast cancer risk. The findings will be used to refine the relevant biomarkers and perform a power analysis for a 5-year clinical trial with breast cancer as an endpoint. Once these biomarkers are validated, other candidate prevention agents for breast cancer could be incorporated into future trials. Significant correlations between SEB and breast cancer incidence will allow clinicians to identify women who can effectively lower their breast cancer risk, potentially with American ginseng. Therefore we will establish a base of comparison between breast cancer patients and participants in the SELF study by collecting anthropometric data (height, weight, body composition, waist-hip ratio), dietary history, exercise habits, and insulin resistance blood panel (HOMA index, leptin, ghrelin, and adiponectin) and calculated 5 year risk of breast cancer (Gail score) in participating breast cancer patients. Contingent on an observed antiproliferative effect of ginseng on tumor or surrounding normal breast tissue in treated breast cancer patients or on the other surrogate markers of breast cancer risk, a breast cancer prevention trial involving exercise with or without ginseng supplementation will be designed.

2.5 Gelatin Encapsulated Standardized Lyophilized Water-Extract of American Ginseng root derived from *Panax quinquefolius*, L. (LEAG)

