3.0 PATIENT SELECTION

3.1 Eligibility Criteria

1. Patients with a cytologically confirmed diagnosis of breast cancer with a biopsy showing invasive or non-invasive breast cancer (DCIS) at least 1.0 cm greatest diameter on imaging (biopsy must have been performed within 6 months of screening visit).
2. Surgical patients, undergoing lumpectomy, subtotal or total mastectomy.
3. Age ≥ 18 years of age.
4. Female.
5. Patients must have tissue blocks available from diagnostic biopsy.
6. Negative pregnancy test, medical history of surgical sterilization, or 1 year post-menopausal. The effects of LEAG on the developing human fetus at the recommended therapeutic dose are unknown. For this reason women of child-bearing potential must agree to use adequate contraception (hormonal or barrier method of birth control; abstinence) prior to study entry and for the duration of study participation.
7. Patient must be willing to forgo surgery for a minimum of 5 days.
8. The ability and willingness to sign a written consent.
9. Patients currently being treated for hypertension must be on a stable dose of medication for the past 30 days.
10. Diabetic patients must be well controlled (HbA1c < 8.5 within past 60 days or documented fasting blood glucose < 140 mg/dl for three consecutive days). Known diabetics who have experienced episodes of symptomatic hypoglycemia in the last 6 months are also considered poorly controlled and will be excluded from study participation.
11. ECOG status of ≤ 2 or Karnofsky $\geq 60\%$ (Appendix F).

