5.0 TREATMENT PLAN

5.1 Screening Procedures

- 5.1.1 History and physical reviewed and recorded, including performance status.
- 5.1.2 Concomitant medications reviewed and recorded.
- 5.1.3 Vital signs reviewed and recorded.
- 5.1.4 Inclusion and exclusion criteria will be reviewed.
- 5.1.5 Review and record available HbA1c status (within past 60 days) or fasting blood glucose values (three consecutive days below 140 mg/dl)
- 5.1.6 Informed consent process
- 5.1.7 Pregnancy test, if required

5.2 Study Visit 1

- 5.2.1 Obtain tissue blocks for immunohistochemistry from core biopsy

- Proliferation Markers: immunohistochemistry for ER, PR, Ki67, cyclin D1, Cox-2, and angiotensin 2.
- Cytotoxicity Markers: cyclin D2 and TUNEL
- Angiogenesis Markers: angiotensin 2

5.2.2 Fasting lab work will be obtained.

Serum for levels of gRc and gRh2, inflammatory mediator proteomic panel (IL1b, IL6, IL8, MCP-1, TNFa, HGF, NGFb, Insulin, and Leptin), pregnancy test (if not already done at screening visit) if woman is of child-bearing potential, HOMA index, leptin, ghrelin, and adiponectin.

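### Two sections name different hospitals for ER, PR and Ki-67 staining, so a patient's before and after slides can come from different laboratories

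*Combined protocol and SAP*

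**What the plan says.** Section 9.1 E covers sections from both the diagnostic biopsy and the resected specimen. It states: "The ER, PR, and Ki67 staining will be done in the pathology department of the hospital where the diagnostic biopsy was performed", and gives the purpose: "in order to optimally compare baseline and treated tumor".

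Section 9.2.2 describes handling of the tissue removed on the day of surgery. There, tumor and normal breast "slides will be stained for ER, PR, and Ki-67 in the pathology dept of the hospital where the surgery takes place".

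Other parts of the plan that bear on this:

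- Section 3.1, criterion 1, on timing: "biopsy must have been performed within 6 months of screening visit". Criterion 5: "Patients must have tissue blocks available from diagnostic biopsy". Neither says where the biopsy must be done.
- Section 5.2.1: "Obtain tissue blocks for immunohistochemistry from core biopsy". ER, PR and Ki67 are among the stains listed, but the section does not say where the core is stained.
- Section 1.1.1 makes the before-and-after comparison the primary objective, using "immunohistochemistry for ER, PR, Ki67, cyclin D1, COX-2".
- Section 16.0 treats each patient as her own control and uses paired t or Wilcoxon signed-rank tests. The synopsis describes a single-center, non-randomized, unblinded trial.

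**The concern.** The two rules identify the hospital by different events, the biopsy and the surgery. They agree only when both happen in the same place. If they do not, and the core is stained under 9.1 E while the operative slides are stained under 9.2.2, the pair is split between two laboratories. That is the situation the stated purpose in 9.1 E is meant to prevent.

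Three of the five tissue markers in Section 1.1.1 are exposed, including Ki-67, on which the rationale in Section 2.6 leans. Any consistent difference between laboratories goes straight into the paired change. It can look like a LEAG effect or conceal one, and enrolling more patients does not remove it.

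An antiproliferative effect on tissue is one of the two triggers in Section 2.4 for designing the prevention trial. The other is an effect "or on the other surrogate markers of breast cancer risk".

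**Working it through.** **Comparing the passages**

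| | Section 9.1 E | Section 9.2.2 |
|---|---|---|
| Stains | ER, PR, Ki67 | ER, PR, Ki-67 |
| Specimens | Biopsy and resected specimen | Tissue from the day of surgery |
| Laboratory | Hospital of the biopsy | Hospital of the surgery |
| Reason given | Best comparison of baseline with treated tumor | None |

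The single-center label does not settle the matter, because a biopsy taken up to six months before screening may have been done elsewhere. For contrast, 9.2.2 sends the surgical sections for cyclin D1, cyclin D2, COX-2 and TUNEL to one laboratory.

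**Illustrating the size**

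The plan has no figure to reproduce. The 25 to 50 patients come from Section 16.1, which ties that number to the time frame of treatment. Everything else is assumed: a two-sided 5% level, 80% reference power, a share *f* of patients with split pairs, and a laboratory shift *d* in units of the SD of the paired change.

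For a shift in one direction and a true LEAG effect of zero:

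- mean paired change = *f* × *d*
- SD = √(1 + *f*(1 − *f*)*d*²)
- noncentrality = √n × mean / SD, with n − 1 degrees of freedom

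Example with *f* = 0.5, *d* = 0.3, n = 25: mean = 0.15; SD = √(1 + 0.25 × 0.09) = 1.011; noncentrality = 5 × 0.15 / 1.011 = 0.742; rejection probability = 0.110.

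| Share *f* | Shift *d* | n=25 | n=50 |
|---|---|---|---|
| 0% | any | 5.0% | 5.0% |
| 10% | 0.3 | 5.2% | 5.5% |
| 25% | 0.3 | 6.5% | 8.1% |
| 50% | 0.2 | 7.7% | 10.6% |
| 50% | 0.3 | 11.0% | 17.7% |
| 50% | 0.5 | 21.4% | 39.0% |
| 100% | 0.3 | 30.2% | 54.8% |

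A separate simulation with other inputs (40,000 runs per setting) shows the same pattern. At *f* = 0.4 and *d* = 0.5 it rejects 14% of the time at n=25 and 26% at n=50.

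**Masking.** The true effect detectable with 80% power is 0.584 SD at n=25 and 0.404 SD at n=50. Let a 0.3 SD shift oppose it, so the mean becomes effect − *f* × 0.3.

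| Share *f* | Power, n=25 | Power, n=50 |
|---|---|---|
| 10% | 75% | 73% |
| 50% | 54% | 41% |

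**Shifts in random directions.** In 100,000 simulated trials per setting with *d* = 0.3, type I error stays at 0.049 to 0.050. Power falls from 0.80 to 0.785 (half affected) or 0.766 (all affected) at n=25, and to 0.782 or 0.764 at n=50.

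**The case against.** The strongest reply is that the problem may never arise in practice. The trial is single-center, and if every biopsy and operation took place in one hospital, the two sentences agree. The text of Section 15.0 (Participating Institutions) was not in the copy reviewed and might settle this. A split pair also needs a mixed reading. Section 9.1 E read alone keeps the pair together, and the study obtains the core blocks, so cores could equally be stained alongside the operative slides. If only 10% of patients are affected, the false-positive rate barely moves. If shifts go in random directions, the loss is a few points of power and not bias.

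All of this limits the likely impact, and the documents do not favor consistent over random shifts. None of it removes the contradiction. The mixed reading is a natural one, because 9.2.2 deals with day-of-surgery tissue, and nothing in the text reviewed rules it out.

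Two smaller points also stand. The count of three out of five follows Section 1.1.1; the synopsis also lists angiopoietin 2 among the primary evaluations, while Section 1.2.1 makes it secondary. And same-laboratory staining does not remove differences between core and excision tissue.

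**Conclusion.** The concern holds: the plan is wrong as written and should be fixed. Confidence is high that the two sections conflict and that following 9.2.2 can defeat the purpose stated in 9.1 E. The size of any resulting bias is unknown. It is zero if no patient has two hospitals, or if both of her slides go to one laboratory anyway.

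Under the assumed 0.3 SD consistent shift, the effect is negligible with one patient in ten affected. It becomes material with half affected, at roughly two to three and a half times the nominal 5% error. These figures rest on assumed shares, shifts, test level and power, and illustrate what an unadjusted single-arm paired analysis cannot absorb. They do not estimate what happened in this trial.

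**What to change.** Replace both sentences with a single rule: for each patient, sections from the diagnostic block and the surgical block are stained for ER, PR and Ki-67 in the same laboratory. Preferably stain the pair in one batch and read it under coded labels. Either hospital's laboratory will do if both blocks go there. Using the study laboratory is optional; for its immunostaining, Section 9.1 E describes antibodies only for COX-2 and cyclin D1.

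The cost is one sentence of protocol text. Core blocks are already required and obtained. A little more core tissue may be used, or some operative material sent to another laboratory.

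Version 1.8 (2018) revised the objectives according to data availability, so staining may already be finished. In that case, record the staining laboratory for each specimen, report the number of split pairs, and add a sensitivity analysis restricted to same-laboratory pairs. That fallback loses precision. If half the pairs are split, the effect detectable with 80% power rises from 0.40 to 0.58 SD (25 of 50 pairs kept), or from 0.58 to about 0.85–0.89 SD (13 or 12 of 25 kept).
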